3.4 Study Population and Criteria

Study Subjects

Inclusion Criteria:

- (1) Age 18–30 years;
- (2) Basically normal diet and sleep;
- (3) No history of mental illness;
- (4) No MRI contraindications (e.g., metal implants or pacemakers) or claustrophobia;
- (5) Willing to participate in this study and sign the informed consent form.

Exclusion Criteria:

- (1) Presence of auricular skin lesions or allergy to adhesive ear patches;
- (2) Currently receiving regular acupuncture treatment;
- (3) History of bleeding disorders or anticoagulant use (increased bleeding risk);
- (4) Previous history of syncope during acupuncture.

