3.2 Study Population and Recruitment

Healthy adults were recruited from Taizhou People's Hospital through hospital outpatient

clinics and promotional posters on the hospital's official WeChat accounts. The study adhered to the principle of voluntary participation, and all subjects were required to sign an informed consent form before enrollment. All participants were assessed and screened by a physician.

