3.5 Randomization and Blinding

The enrolled 32 subjects were randomly assigned in a 1:1 ratio to two groups: the real auricular acupuncture vagus nerve stimulation group (AA) and the sham auricular acupuncture control group (SA).

This study employed a double-blind design, meaning that neither the subjects in each group nor the acupuncturist knew whether they belonged to the AA group or the SA group.

The sham stimulation group used press needles without tips at the same acupoints, preventing the subjects from distinguishing whether they were receiving real or sham stimulation, thereby reducing expectancy effects. Randomization and allocation concealment were performed by an independent statistician, ensuring that neither the study participants nor the researchers could influence the assignment. The success of participant blinding was assessed using the Bang Blinding Index (BBI); blinding was considered successful when the BBI value was between -0.2 and 0.2.

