3.6 Interventions

3.6.1 Auricular Press Needle Acupuncture

Auricular Points: Heart, Kidney, Shenmen, Subcortex

① Before the application, the participants rested for 5 min, followed by baseline fMRI examination (including T1-weighted and T2-weighted images).

② After the examination, auricular press needles were inserted. The physician's hands and local acupoint areas were routinely disinfected. The experimental group used Dingshi brand disposable sterile press needles (with release paper, Medical Device Registration No.: Su Xie Zhu Zhun 20212200040, specification 0.20×1.3 mm). Disposable, sterile press needles without tips were used in the control group. The needle body was inserted at the aforementioned points, the release paper was removed, and the adhesive tape was gently pressed to ensure tight adhesion. Both ears were treated at each time-point.

③ After application, each acupoint was pressed 20 times. Pressing all eight points twice took approximately 2 min to complete. Rest for 10 min. A second pressing session was performed for 2 min. Rest for 10 min. A third pressing session was performed for 2 min, and the press needles were removed. (Total duration: approximately 26 min).

④ Immediately an fMRI examination (T2-weighted images only) was performed to observe changes in brain regions.

The intervention involved applying auricular press needles (a type of intradermal embedding needle) to specific acupoints.

[figure not shown]

Figure 1. Localization of selected auricular points.

Table 1. Common names, locations, and indications of auricular points.

Common Name	Acupuncture Point	Anatomical Location	Indications Based on TCM and Scientific Research	Mental Health and Depression Indications
Shenmen	TF4	The upper portion of the apex of the triangular fossa is closer to the upper branch of the antihelix.	Analgesic and anti inflammatory action is the most critical anesthesia point on the ear.	Sedative point. Calms the mind.
Heart	CO15	In the center of the cavum conchae	Used for cardiac complaints such as angina, cardiac rhythm disorders	Indicated for anxiety, depression, distress, mental agitation, and insomnia.
Kidney	CO10	In the cymba conchae, in a groove below the start of the inferior crus.	Used for issues in the urinary and genital systems. Assists with tinnitus, auditory conditions, and sleep disorders.	Indicated for fear, insecurity, and lack of willpower.

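### The acupuncture exclusion stops at current, regular treatment, so people who have already felt ear press needles can enrol in a trial whose sham depends on participants not recognising a tipless one

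*Combined protocol and SAP*

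**What the plan says.** Two exclusion criteria in section 3.4 touch on acupuncture history. Criterion (2) is "Currently receiving regular acupuncture treatment". Criterion (4) is "Previous history of syncope during acupuncture", a safety rule that removes only people who fainted.

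Section 3.2 gives the source of participants: "Healthy adults were recruited from Taizhou People's Hospital through hospital outpatient" "clinics and promotional posters on the hospital's official WeChat accounts". On screening it says "All participants were assessed and screened by a physician", without listing what was asked.

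Section 3.5 describes the control: "The sham stimulation group used press needles without tips at the same acupoints, preventing the subjects from distinguishing" real from sham. The stated purpose is to reduce expectancy effects. Success is judged by the Bang Blinding Index, with -0.2 to 0.2 counted as successful. Section 3.6.1 gives the active device as a press needle, "specification 0.20×1.3 mm", inserted at four points on each ear and pressed in three sessions.

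The primary outcome in section 3.7 is the T1-T0 change in insula-mPFC connectivity. The baseline data listed there are demographics, the scan and a clinical assessment.

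**The concern.** Criterion (2) is narrowed by two words: treatment must be both current and regular. A person who finished a course last week, or who has had ear press needles now and then, passes it. Criterion (4) shows that people with past acupuncture could come to screening, although it says nothing about how many.

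The two arms use the same points and the same procedure, and differ in whether the needle has a tip. The comparison is therefore only as good as participants' inability to tell the devices apart. Someone who has felt a real press needle has a reference sensation that a newcomer lacks. If such people recognise what they receive, those in AA will expect an effect and those in SA will not. Randomisation does not remove this, because the expectancy runs in opposite directions in the two arms even when the numbers are equal.

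A second, weaker worry is that a recent user's T0 scan could still reflect earlier stimulation. T0 enters the primary outcome directly.

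**Working it through.** **1. Does any other part of the plan close the gap?** The relevant sections, side by side:

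- 3.2: a physician screens; no acupuncture-history item is described.
- 3.4: criterion (2) covers current regular treatment, criterion (4) covers fainting. There is no washout and no requirement to be new to ear acupuncture.
- 3.5: 1:1 allocation; no stratification by past exposure is stated.
- 3.7: past exposure is not among the listed baseline data.
- 3.8.2: unadjusted two-group tests; no covariate for past exposure.

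So the plan as written neither prevents the problem nor records it.

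**2. What could it do to the blinding check?** The plan gives no figure to reproduce here beyond its ±0.2 band. Inputs from the documents: 16 per arm (3.3) and the band (3.5). Assumptions: everyone guesses real or sham, k participants in an arm are always right, and the other 16 - k guess 50:50.

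For one arm, BBI = (correct - incorrect)/16 = 2 × correct/16 - 1. Expected correct = k + (16 - k)/2. Hence expected BBI = 2[k + (16 - k)/2]/16 - 1 = k/16. Each certain recogniser adds 1/16 = 0.0625.

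Exact binomial probabilities for one arm, with X ~ Bin(16 - k, 0.5) and correct = k + X. The index lies inside the band when correct is 7, 8 or 9, and above 0.2 when correct is 10 or more:

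| k | expected BBI | P(inside band) | P(BBI > 0.2) |
|---|---|---|---|
| 0 | 0 | 0.55 | 0.23 |
| 2 | 0.125 | 0.52 | 0.40 |
| 3 | 0.19 | 0.45 | 0.50 |
| 4 | 0.25 | 0.37 | 0.61 |
| 6 | 0.375 | 0.17 | 0.83 |

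**3. How large might k be?** The documents do not say. If 10%, 25% or 40% of participants had used acupuncture before (assumed), the expected number per arm would be 16 × 0.10 = 1.6, 16 × 0.25 = 4 or 16 × 0.40 = 6.4. These are ceilings for k, not estimates of it: only those who have felt ear press needles have the relevant experience, and they may not recognise the device with certainty. More generally, if m experienced participants in an arm are each right with probability p, expected BBI = m(2p - 1)/16. This equals m/16 at p = 1 and falls to 0 at p = 0.5.

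**4. Would chance spread previous users unevenly?** This matters for carry-over. With K previous users among 32 (assumed) and x of them in AA, x is hypergeometric and the arms differ by |2x - K|. The probability of a difference of at least 4 is 0.10, 0.17, 0.22 and 0.25 for K = 4, 6, 8 and 10.

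**5. What could a comparison restricted to newcomers show?** At two-sided 0.05 and 80% power, the detectable standardised difference is (1.96 + 0.84) × √(2/n). With n = 16 this is 0.99. If four per arm were set aside, n = 12 and it is 1.14.

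**The case against.** The strongest reply is that the consequences are conjecture. Section 3.5 says the tipless needle works by "preventing the subjects from distinguishing whether they were receiving real or sham stimulation, thereby reducing expectancy effects", and nothing in the documents shows otherwise. A reader might infer that anyone who has felt a press needle can tell the two devices apart. The documents do not support that; they support only that such people may be better placed to do so.

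A reader might also count every previous acupuncture user as a recogniser. That does not follow either: body acupuncture gives no experience of ear press needles, and among healthy adults aged 18-30 the relevant group could be small. Under the 10% assumption the expected index stays inside the band even with certain recognition. With no recognisers at all, an arm falls inside the band only 55% of the time, so an index outside it would be weak evidence that previous users were the cause. That imprecision is a separate limitation of the check, and changing eligibility does not cure it.

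On carry-over, a reader might infer a biased AA-SA contrast. The documents give no duration of effect. The repeated-treatment connectivity results cited in the background come from taVNS in patients, not from past acupuncture in healthy people. Randomisation balances previous users in expectation, and a stable residual effect would be present at both T0 and T1 and so largely cancel.

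All of this limits the size of the point. What remains is that the eligibility gap is real, nothing else closes it, and balance between arms does not protect against expectancies that run in opposite directions. The index measures unblinding afterwards without preventing it: with two certain recognisers in an arm, that arm still falls inside the band with probability 0.52.

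**Conclusion.** The point holds as a cheap improvement to the protection of blinding, not as a demonstrated flaw in the result. Exclusion (2) admits people with past ear press-needle experience and people with recent or occasional acupuncture, and past exposure is not among the listed data.

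The possible size is k/16 on the expected Bang index, crossing the plan's limit between k = 3 (0.19) and k = 4 (0.25). This rests on certain recognition by k people, 50:50 guessing by the rest, and no undecided answers. The value of k is unknown and may be well below the number of previous users. No effect on the primary outcome can be computed from the documents.

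Carry-over into T0 is an unquantified possibility. It would mainly add noise, with some room for chance imbalance at 16 per arm.

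**What to change.** Extend exclusion (2) to any previous auricular press-needle or ear-acupuncture treatment, and to any acupuncture or auricular stimulation within a look-back window before T0. The investigators should set the window; the documents support no particular length. Ask about both at the physician screening and record the answers.

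The cost is a revised criterion, a screening question and a slightly smaller recruitment pool, which should be manageable for 32 healthy adults aged 18-30.

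Sections 3.2 and 3.3 describe recruitment in the past tense, so enrolment may already be complete. In that case, obtain prior ear-acupuncture exposure (type and recency) where possible, bearing in mind that it may never have been collected, and report it by arm beside the Bang index. A comparison restricted to participants with no such exposure can be added, but should be labelled supportive only: with fewer than 16 per arm it could reliably detect only differences of about one standard deviation or more.

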3.5 Randomization and Blinding

The enrolled 32 subjects were randomly assigned in a 1:1 ratio to two groups: the real auricular acupuncture vagus nerve stimulation group (AA) and the sham auricular acupuncture control group (SA).

This study employed a double-blind design, meaning that neither the subjects in each group nor the acupuncturist knew whether they belonged to the AA group or the SA group.

The sham stimulation group used press needles without tips at the same acupoints, preventing the subjects from distinguishing whether they were receiving real or sham stimulation, thereby reducing expectancy effects. Randomization and allocation concealment were performed by an independent statistician, ensuring that neither the study participants nor the researchers could influence the assignment. The success of participant blinding was assessed using the Bang Blinding Index (BBI); blinding was considered successful when the BBI value was between -0.2 and 0.2.

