3.3 Sample Size

The sample size estimation for functional MRI (fMRI) studies was based on Desmond's research findings. When analyzing fMRI data using a liberal threshold of 0.05, at least 12 subjects are required to achieve 80% or higher activation intensity at the single-voxel level [11]. This study randomly recruited 32 subjects, with 16 subjects per group, to systematically analyze changes in brain function before and after auricular acupuncture intervention, combined with its efficacy.

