3.7 Observational Indicators

Resting-state functional magnetic resonance imaging was used to conduct pre- and post-intervention comparative analyses in participants receiving auricular acupuncture.

Data collection is divided into two stages:

Baseline: Collection of demographic data, baseline fMRI scan, and clinical assessment (T0).

post-intervention:fMRI scan and clinical assessment immediately after the intervention (T1).

Primary Outcome Measure

Functional connectivity strength between the insula and the medial prefrontal cortex (MPFC)(T1-T0)

This connectivity strength serves as a proxy for the efficiency of information exchange between the “interoceptive hub” and “the self-referential/emotion-regulatory hub”. An increase following auricular acupuncture may reflect enhanced psychosomatic integration and top-down emotional regulation, suggesting a functional optimization of this circuit. Conversely, a decrease could indicate a disruption of pathological hyper-connectivity related to emotional constraint or an upregulation of control—mechanisms consistent with the observed alleviation of emotional symptoms

Secondary Outcome Measures

①Local brain activity indicators:regional homogeneity (ReHo), amplitude of low-frequency fluctuation (ALFF), fractional ALFF (fALFF)(T1-T0);

ReHo captures the temporal synchrony of neural activity within local brain regions. Following auricular acupuncture, increased ReHo in regions such as the insula and prefrontal cortex may reflect improved neural coordination and functional integration. Conversely, decreased ReHo in specific areas could indicate a modulatory effect on abnormally elevated local synchrony.

ALFF reflects the intensity of spontaneous neural activity in the brain. An increase in ALFF within emotion- and cognition-related regions following auricular acupuncture may indicate an elevation in baseline neural activity or metabolic activity in these areas. Conversely, a decrease in ALFF in regions such as the limbic system could reflect an

inhibitory modulatory effect of the intervention on hyperactivity, potentially contributing to emotional stabilization.

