3.8.2 Clinical Data

Datasets: Intent-to-Treat (ITT) and Per-Protocol (PP) analyses were used.

Normally distributed continuous data were described as mean \pm standard deviation, and inter-group comparisons for normally distributed variables used independent-samples t-tests. Non-normally distributed scale data will be described as medians and interquartile ranges, and the Mann–Whitney U non-parametric test will be used for statistical analysis. Categorical data were analyzed using the Chi-square test.

All statistical analyses were performed using SPSS or R software. Statistical significance was set at $P < 0.05$.

四、Ethics and Participant Protection

Before the study begins, the study protocol (including questionnaires and the informed consent form) will be submitted for review and approval to the Ethics Committee of Taizhou People's Hospital Affiliated to Nanjing Medical University (ethics number: LSKY 2025-175-01). Any amendments to the study protocol will be submitted to the Ethics Committee for approval and record-keeping. All participants will be fully informed about the study purpose, procedures, potential risks, and benefits, and will provide written informed consent.

五、References

- [2] de Oliveira Rodrigues DM, Menezes PR, Machado Ribeiro Silotto AE, et al. Efficacy and Safety of Auricular Acupuncture for Depression: A Randomized Clinical Trial [J]. *JAMA Netw Open.* 2023;6(11):e2345138.

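### With 16 participants per arm, a Bang index point estimate inside or modestly outside ±0.2 cannot settle whether blinding worked, and no confidence interval is planned

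*Combined protocol and SAP*

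**What the plan says.** Section 3.5 states: "The success of participant blinding was assessed using the Bang Blinding Index (BBI"). The criterion follows directly: "blinding was considered successful when the BBI value was between -0.2 and 0.2". The rule speaks of one value, although the standard index is calculated separately in each arm. The section does not give the response options or the time at which participants are asked.

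Section 3.3 sets the size at 32 participants, "with 16 subjects per group". The reason given is a voxel-level fMRI rule ("at least 12 subjects are required to achieve 80% or higher activation intensity at the single-voxel level"), not the precision of a blinding index.

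Section 3.8.2 does not mention the BBI or any interval for it. The nearest provision is general: "Categorical data were analyzed using the Chi-square test". Section 3.7 lists a post-intervention "fMRI scan and clinical assessment immediately after the intervention (T1") but does not name the treatment guess among the data collected.

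**The concern.** The rule turns an estimate from 16 people into a verdict. If the sampling error of the index is large compared with the width of the ±0.2 band, the verdict depends heavily on chance. A well-blinded arm can miss the criterion, and an arm with real but modest unblinding can meet it.

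The stake is the credibility of the sham control. Section 3.5 relies on participants being unable to tell tipless from real press needles, and the BBI is the only planned check of that. A reader told that blinding succeeded would take more reassurance than 16 answers per arm can give. A reader told that the criterion was missed might discount the comparison without good reason.

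**Working it through.** **Inputs from the document.** Limits of ±0.2 and 1:1 allocation (section 3.5); 16 per arm (section 3.3). The ±0.2 limits come with no derivation, so there is no figure of the plan's own to reproduce.

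**Assumptions, because the document is silent.** Standard per-arm index; all 16 evaluable; guesses split evenly between right and wrong when blinding is perfect; a don't-know (DK) share of 0%, 25% or 50%; 95% confidence.

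**Formulas.** Per arm, BBI = (correct − incorrect)/n. Its variance is [(1 − DK) − BBI²]/n. An arm passes if |BBI| ≤ 0.2, which at n = 16 means that correct and incorrect answers differ by at most 3.

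**1. Which results pass.** With no don't-knows the index moves in steps of 2/16 = 0.125, so only 7, 8 or 9 correct pass. Exact (Clopper-Pearson) 95% limits on the BBI scale are:

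| Correct of 16 | BBI | Meets rule | 95% CI |
|---|---|---|---|
| 8 | 0 | yes | -0.51 to 0.51 |
| 9 | 0.125 | yes | -0.40 to 0.60 |
| 10 | 0.25 | no | -0.29 to 0.70 |
| 11 | 0.375 | no | -0.17 to 0.78 |
| 13 | 0.625 | no | 0.09 to 0.92 |
| 14 | 0.75 | no | 0.23 to 0.97 |

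One extra correct guess, from 9 to 10, changes the verdict on almost the same evidence. A perfectly even split still leaves values up to about 0.5 open. From 14 correct upwards the lower limit exceeds 0.2, so clear unblinding is detectable.

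**2. A randomly guessing arm (true BBI = 0).** With no don't-knows, P(7, 8 or 9 correct) = (11440 + 12870 + 11440)/65536 = 35750/65536 = 0.5455, so P(outside) = 0.4545. Counts of 5, 6, 10 or 11 contribute 2 × (8008 + 4368)/65536 = 0.3777 of this, or 83% of the chance misses. Their 95% intervals all include 0, so an interval would show them to be inconclusive.

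Exact trinomial sums give the other columns. Pooling and the both-arms requirement are alternative readings that the document does not state.

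| Chance of falling outside | 0% DK | 25% DK | 50% DK |
|---|---|---|---|
| One arm, n = 16 | 0.454 | 0.315 | 0.215 |
| At least one of two arms, if both must pass | 0.702 | 0.531 | 0.384 |
| All 32 answers pooled (not the standard index) | 0.215 | 0.185 | 0.103 |

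The one-arm figure falls to 0.164 at 60% and 0.107 at 70% don't-know.

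**3. An arm that is partly unblinded.** Probability that one arm meets the rule:

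| True BBI | 0% DK | 25% DK | 50% DK |
|---|---|---|---|
| 0.3 | 0.289 | 0.331 | 0.301 |
| 0.4 | 0.168 | 0.171 | 0.107 |
| 0.5 | 0.078 | 0.062 | 0.011 |

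**4. Precision needed to support a claim that |BBI| is below 0.2.** At BBI = 0 the Wald half-width is 1.96 × √((1 − DK)/n). At n = 16 this is 0.49, 0.42 or 0.35. Setting it to 0.2 gives n = (1.96/0.2)² × (1 − DK) = 96.04, 72.03 or 48.02, that is 97, 73 or 49 per arm. At 16 per arm the interval fits inside ±0.2 only with at least 14 don't-knows (half-width 0.212 at 13, 0.173 at 14), where the Wald interval is itself unreliable.

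**The case against.** The strongest reply is that little depends on this. The BBI triggers no exclusion, adjustment or sensitivity analysis. That is true, and it caps the point at minor.

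Second, section 3.5 offers a working convention. It does not claim that a small index has been proved, and it does not say in words that a value outside the limits means blinding failed. That is fair as to wording. Still, a criterion for success will be read as not met when the estimate lies outside it, and a pass will be reported as success.

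Third, the error rates depend on a don't-know share and a per-arm reading that the document does not give. This also stands: with a large don't-know share or pooled answers, the chance of a false miss drops to about 10%. But a true BBI of 0.3 still passes in roughly three cases in ten at each share from 0% to 50%.

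Fourth, the guess item, its options and its timing may be in the questionnaires mentioned in the ethics section, and the T1 clinical assessment is not itemised. The silence on these details is therefore weak evidence that they were not planned. It does not supply the missing interval.

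Finally, section 3.5 is written in the past tense, so guesses may already exist. Setting aside a stated criterion at that stage would be a post hoc change and should be declared as one.

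**Conclusion.** The concern holds, as a minor point. With 16 per arm, a BBI within ±0.2 does not establish successful blinding, and one modestly outside does not establish failure. Under the stated assumptions the rule misclassifies a randomly guessing arm in 22% to 45% of cases and passes an arm with true BBI 0.3 in 29% to 33%. It performs acceptably against strong unblinding: a true BBI of 0.5 passes in only 1% to 8%. The lack of precision holds across don't-know shares of 0% to 50%; the exact rates depend on a share that the document does not give. The consequence is confined to what the trial can say about participant blinding.

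**What to change.** In section 3.5, replace the pass/fail sentence with wording such as:

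> The BBI will be reported separately for AA and SA, with 95% confidence intervals and the numbers of correct, incorrect and (if offered) don't-know guesses. The response options and the time of asking will be stated. The two values will be read together: both near 0, guesses consistent with chance; AA positive and SA negative, most in both arms believed they had real needles; both positive, guesses track allocation. The range -0.2 to 0.2 is a descriptive reference only, because 16 per arm is in general too few to show that the absolute BBI is below 0.2.

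The cost is protocol wording, two confidence intervals and one small table, with no new participants. If guesses have already been collected, the change affects analysis and reporting only; it should be dated and declared, and the result against the stated range can still be shown beside the intervals. Don't-know counts will exist only if that option was offered. What is given up is the ability to declare blinding successful from a point estimate.

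### Section 3.5 judges blinding by one BBI value, but the index gives one value per arm and the plan never compares belief between the arms

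*Combined protocol and SAP*

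**What the plan says.** Section 3.5 (Randomization and Blinding) holds everything the plan says about testing the blind. Participants' blinding is assessed with the Bang Blinding Index, and the rule is that "blinding was considered successful when the BBI value was between -0.2 and 0.2". The same section gives the purpose of the sham: "preventing the subjects from distinguishing whether they were receiving real or sham stimulation, thereby reducing expectancy effects". Section 3.6.1 describes the device: "Disposable, sterile press needles without tips were used in the control group". Section 3.3 sets the size: "This study randomly recruited 32 subjects, with 16 subjects per group".

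The text does not say whether the range applies to each arm, to both arms jointly or to a combined value. It does not say when guesses are taken, whether don't-know is an allowed answer, or how the two arms are to be compared. The analysis text in section 3.8.2 does not mention the index.

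**The concern.** The Bang index is calculated within an arm, as correct guesses minus incorrect guesses. A two-arm trial therefore yields two values, and a rule about a single value is incomplete until the plan says how they are combined.

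The rule also looks at the wrong quantity for its stated purpose. Expectancy distorts a parallel-group contrast when the share believing they had real needles differs between AA and SA. If the sham is convincing, most people in both arms will believe their needles were real. The AA index is then positive, the SA index is negative, and belief is balanced. The design aims at this: a tipless needle at the same points, with one pressing procedure described for both groups.

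At stake is the blinding verdict, and so how far an AA–SA difference in insula–mPFC connectivity can be attributed to the needle rather than to expectation. Neither more participants nor an interval around each index would solve this, because the limits do not measure the gap.

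**Working it through.** **Inputs.** Limits −0.2 to 0.2 (section 3.5); 16 per arm (section 3.3); 1:1 allocation (section 3.5). The limits are a chosen convention with no stated derivation, so there is no plan figure to reproduce. The following are assumptions, not document text: the standard per-arm definition of the index, independent guesses, and either forced choice or a don't-know option, as marked.

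**Formulas.** Let p be the share in an arm who believe they had real needles. With forced choice:
- BI(AA) = 2p(AA) − 1
- BI(SA) = 1 − 2p(SA)
- Belief gap p(AA) − p(SA) = [BI(AA) + BI(SA)] / 2

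The same identity holds with don't-know answers if each counts as half.

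**Range applied to each arm**

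| Belief AA / SA | BI(AA) / BI(SA) | Gap | Verdict |
|---|---|---|---|
| 60% / 60% | +0.2 / −0.2 | 0 | on the limit |
| 70% / 70% | +0.4 / −0.4 | 0 | unsuccessful |
| 75% / 75% | +0.5 / −0.5 | 0 | unsuccessful |
| 60% / 40% | +0.2 / +0.2 | 20 points | on the limit |

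Equal belief passes only between 40% and 60%.

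**What can be observed at 16 per arm**
- Forced choice: the index moves in steps of 2/16 = 0.125. Only 7, 8 or 9 correct guesses pass (−0.125, 0, +0.125). The largest passing gap is 9/16 − 7/16 = 12.5 points.
- Don't-know allowed and scored as half: the largest passing index is 3/16 = 0.1875 in each arm, so the largest passing gap is 18.75 points.
- Don't-know allowed, counting only those who say real: 25 points can pass. Example: AA 9 real, 6 sham, 1 don't know; SA 5 real, 8 sham, 3 don't know. Both indices are 3/16 = 0.1875, and 9/16 − 5/16 = 0.25.

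**Probability that both arms pass** (exact binomial, forced choice, 16 per arm)
- True belief 60% / 60%, gap 0: 0.4145² = 0.172.
- True belief 60% / 40%, gap 20 points: also 0.172. The rule cannot tell these two apart.
- True belief 70% / 70%, gap 0: 0.1682² = 0.028.
- True belief 50% / 50%, pure guessing: 0.5455² = 0.298.

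**Two indices averaged.** By the identity above, the average equals the belief gap. Then 70% / 70% gives 0 and passes, while 60% / 40% gives 0.20, on the limit. The first result is the reverse of the per-arm verdict on identical data.

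**Precision.** The 95% half-width for one arm's index near 0 is 1.96 × 2 × √(0.25/16) = 0.49. For the AA–SA difference in belief near 50% it is 1.96 × √(2 × 0.25/16) = 0.35.

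**The case against.** Four points can be made for leaving the rule alone.

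1. The plan does not state the per-arm reading, and if the indices were averaged, equal belief would pass. This stands. It rules out saying flatly that a convincing sham is called a failure. It leaves the plan with an unstated choice that can reverse the verdict.

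2. A gap of exactly 20 points cannot pass at the planned size with forced choice, since an index of 0.2 would need 9.6 correct guesses out of 16. This also stands. Twenty points is the limit of the rule, and the gaps that can pass in this trial are those in the working.

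3. Equal belief from 40% to 60% passes, and failing stronger shared belief is a cautious error. This is true, but passing a genuine gap is not cautious, and the same limits do both.

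4. No analysis or exclusion in the documents depends on the verdict, the primary outcome is imaging rather than self-report, and the gap can be recovered if both indices are reported. This limits the consequence. But the plan itself gives expectancy as the reason for the sham, and it does not commit to reporting both indices.

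A replacement rule is also open to challenge. Qualifying conclusions when the gap is large would leave large undefined, and at ±35 points a 20-point gap could not be told from zero. This stands as well, and it is why the fix sets no new threshold.

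**Conclusion.** The point holds in a limited form. The plan gives one range for one value when the index produces two, does not say how they combine, and does not compare belief between arms. On the natural per-arm reading, the rule followed exactly can reject balanced belief above 60% and accept a gap of up to 20 points (12.5 with forced choice, or about 19 with don't-know scored as half, at 16 per arm). On the averaged reading, balanced belief passes.

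A reader might infer more than this, and the documents do not support it:
- That this sham would be reported as failed blinding. The plan gives no expected share of believers and does not state the per-arm reading.
- That a 20-point gap would pass in this trial. That depends on arm size and on how don't-know answers are handled.
- That the primary estimate is biased. The defect concerns the blinding statement that supports interpretation; the AA–SA estimate itself is unchanged.

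This is a cheap improvement. It rests on the standard per-arm definition of the index and on the guessing assumptions listed in the working.

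**What to change.** In section 3.5:
- Report the BBI for AA and SA separately, each with a 95% CI, as description.
- Base the blinding statement on the AA–SA difference in the proportion believing they had real needles, with its 95% CI.
- Fix the handling of don't-know answers in advance, for example scored as half, with a sensitivity analysis counting only those who say real. Also state when guesses are taken.
- State that opposite-signed indices of similar size mean balanced belief, not failed blinding.
- Drop the single-value success rule. If the sponsor keeps any range, say how the two indices enter it.

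The cost is a few lines of plan text and one difference in proportions, from guesses that the BBI already requires. The downside is precision: about ±35 points at 16 per arm. The result should therefore be worded descriptively and cautiously, and the trial gives up a pass/fail claim about blinding.
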